## 8.3 Number of Subjects

Per Agency's recommendation, a McNemar Test has been used for sample size calculation. In the Phase I/II study, the response rates for Weeks 8 through 12 were from 70-100% for wounds randomized to B-VEC and 0-33% for wounds randomized to placebo, respectively. Therefore, assuming a response rate of 75% among wounds randomized to B-VEC and a response rate of 25% among wounds randomized to placebo, with 90% power and a two-sided Type 1 error rate of 5%, 24 subjects (i.e., 24 wound pairs) are required.

## 8.4 Data Management

Pre-designed CRFs are used to collect information for safety and proof of mechanism analyses. An electronic CRF (eCRF) is managed and maintained by the Sponsor for this study. The eCRF is constructed based on the CRF data entry requirements of the protocol. Data queries are generated and resolved within the eCRF. In addition, range checks of the eCRF fields, plausibility and consistency checks across eCRF pages will be performed to assess consistency, accuracy and completeness of the data collected and entered into the eCRF. Standard SAS datasets are generated and provided for analysis.

## 8.5 Analysis Populations

### Safety Population

This population is defined as all subjects who were administered with either B-VEC or placebo. Safety population will be used for all the safety analyses.

### Intent-to-Treat Population

The intent-to-treat (ITT) population includes subjects whose primary wounds were randomized with or without either B-VEC or Placebo administration. ITT population will be used for all the primary and secondary efficacy sensitivity analyses and baseline summaries.

### Modified Intent-to-Treat Population

The modified intent-to-treat (mITT) population includes subjects whose primary wounds were randomized and received B-VEC treatment with at least one post baseline primary endpoint assessment. The mITT population will be used for all the primary and secondary efficacy analyses.

### Per Protocol Population

The per-protocol (PP) population includes all the safety population subjects who completed the study without major protocol deviations. PP population will be used for all the primary and secondary efficacy sensitivity analyses.

## 8.6 Demographic and Baseline Characteristics

The descriptive summaries of subjects' demographic and baseline characteristics are presented by treatment, where applicable, for the safety, ITT, mITT and PP populations. A detailed description of subject disposition is provided.

Subject characteristics include a summary of the following:

- Subject demographics
- Baseline disease characteristics
- Pre-existing medical conditions

Continuous variables are summarized using number of observations, mean and standard deviation, median, and minimum and maximum values. Categorical values are summarized using number of observations and percentages.

Medical History and AEs will be summarized by MedDRA System Organ Class and Preferred Term.

## 8.7 Efficacy Analyses

### 8.7.1 General Approach

The study has a complete randomized-block design in which each subject serves as a block to receive all of the treatment conditions. In this study, each subject provides at least one pair of target wounds with one wound from each pair being treated with B-VEC and the other wound from each pair with placebo in the primary target wound pair. Efficacy measurements are taken multiple times (or repeatedly) over the on-treatment period from each subject.

All data will be presented using summary statistics or frequency tables, as appropriate, and will be analyzed for superiority comparisons between B-VEC and placebo treatments. The description of the sample will be done using summary statistics (n, mean, standard deviation, median, and maximum/minimum) for continuous data and using frequency statistics (counts and percentages) for categorical data. Hypothesis

testing, unless otherwise indicated, will be performed at the 5% significance level (1-sided). All P-values will be rounded to four decimal places; P-values less than 0.0001 will be presented as '<0.0001' in all tables. Unless specifically stated, all confidence intervals will be two-sided with 95% coverage.

Efficacy measures collected pre-dosing at Screening or Visit 1 (Week 1) will be considered as the baseline measurement in this study.

The Sponsor, or their designee, will analyze the data using SAS® Statistical Analysis System Version 9.1.3 or higher. Detailed descriptions of the statistical analysis methods, data conventions, and sensitivity analysis, as well as handling of missing data for both efficacy and safety measures will be described in detail in the Statistical Analysis Plan (SAP).

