### 8.1 Primary Efficacy Endpoint

The following hypothesis for the primary endpoint of the proportion of DEB wounds sites with complete wound healing (CWH) from baseline in B-VEC versus placebo treated intra-subject wound sites at Weeks 22 and 24 or 24 and 26 as determined by the Investigator will be tested:

Null Hypothesis            H0: %CWH in B-VEC = %CWH in Placebo

Alternate Hypothesis    H1: %CWH in B-VEC > %CWH in Placebo

Where % CWH is the percentage of primary wounds with a complete wound healing from baseline at Week 22 and 24 or 24 and 26. A two-sided significance level of 0.05 is considered.

The complete wound healing is defined as 100% wound closure from the exact wound area selected at baseline, specified as skin re-epithelialization without drainage. If new neighboring wounds form around the

original traced baseline wound during the primary evaluation time points, these areas will not be included in the evaluation.

The primary endpoint is defined as wounds that meet any of the following conditions:

- Healed on Week 22 and Week 24, or
- Healed on Week 24 and Week 26.

Only wounds that are healed for at least two (2) consecutive weeks are counted as positive responses.

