6.3 Treatment Compliance and Exposure

Exposure summary by treatment group (primary wounds only) will be presented for the Safety, mITT, and PP populations. The distribution of subjects by the total number of weeks on therapy (0 through 26) will be presented. For the Safety population, the summary of exposure will be based on the actual treatment received.

Treatment compliance is defined as the number of wound treatment doses (active and placebo) actually received divided by the number of doses expected ($\times 100$) over the time period defined by the first and last treatment dose dates. Descriptive statistics for treatment compliance and the number and percentage of

subjects at least 90% compliant will be presented by treatment group (primary wounds only) for the Safety, mITT, and PP populations.

7 Efficacy Analyses

All data will be presented using summary statistics or frequency tables, as appropriate, and will be analyzed for superiority comparisons between B-VEC and placebo treatments. The description of the sample will be done using summary statistics (n, mean, standard deviation, median, and maximum/minimum) for continuous data and using frequency statistics (counts and percentages) for categorical data. Hypothesis testing, unless otherwise indicated, will be performed at the 5% significance level (2-sided). All P-values will be rounded to four decimal places; P-values less than 0.0001 will be presented as '<0.0001' in all tables. Unless specifically stated, all confidence intervals will be two-sided with 95% coverage.

Efficacy measures collected pre-dosing at Screening or Visit 1 (Week 1) will be considered as the baseline measurement in this study.

The Sponsor, or their designee, will analyze the data using SAS® Statistical Analysis System Version 9.4 or higher.

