7.2 Primary Efficacy Analysis

The primary efficacy analyses will use the ITT population and the Primary Wound Pair.

The primary endpoint is the proportion of DEB primary wound sites with complete wound healing from baseline in B-VEC-treated and placebo-treated intra-subject wound sites at Weeks 22 and 24 or 24 and 26, as determined by the Investigator. Complete wound healing is defined as 100% wound closure from the exact wound area selected at baseline, specified as skin re-epithelialization without drainage:

The primary endpoint is defined as responder wounds that meet any of the following conditions:

- Healed on Week 22 and Week 24, or
- Healed on Week 24 and Week 26

Only wounds that are healed for at least two (2) consecutive weeks are counted as positive responses. The primary endpoint response data will be summarized descriptively by the wound treatment.

A summary of the outcomes for each member of the Primary Wound Pair can be represented in the following 2x2 table, where each entry represents a subject. T is the total number of subjects in the ITT population and each cell entry is the number of subjects with the corresponding outcomes of the Primary Wounds.

		Placebo		Row total
		Complete Wound Healing	No Complete Wound Healing	
B-VEC	Complete Wound Healing	A	B	N1
	No Complete Wound Healing	C	D	N2
Column total		M1	M2	T

The null hypothesis of interest is the absence of a treatment effect on wound healing and the alternative hypothesis is the presence of a treatment effect on wound healing.

These hypotheses are equivalent to the following null and alternative hypotheses:

Null Hypothesis H0: Prob(B) = Prob(C)

Alternate Hypothesis H1: Prob(B) ≠ Prob(C)

Where Prob(B) and Prob(C) are the probability of the occurrence of discordant pairs B (B-VEC=Positive & PBO=Negative) and C (B-VEC=Negative & PBO=Positive).

The null hypothesis will be tested by a McNemar test statistic using a two-sided type I error rate of 0.05:

$$\chi^2_{\text{McNemar}} = (B - C)^2 / (B + C)$$

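### Protocol 8.7.1 defaults to a 1-sided 5% test and SAP section 7 to a 2-sided 5% test, so the pain endpoint has two thresholds for nominal significance

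*Protocol*

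**What the plan says.** **Defaults.** Protocol 8.7.1 (General Approach): "testing, unless otherwise indicated, will be performed at the 5% significance level (1-sided". The opening of SAP section 7 (Efficacy Analyses): "Hypothesis testing, unless otherwise indicated, will be performed at the 5% significance level (2-sided". Apart from the sidedness the two sentences match. Protocol 8.7.1 goes on to require two-sided 95% confidence intervals, and so does the SAP.

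**Primary and key secondary endpoints.** Protocol 8.1 has its own statement: "A two-sided significance level of 0.05 is considered". Protocol 8.2 repeats it for the key secondary endpoint. SAP 7.2 agrees: "The null hypothesis will be tested by a McNemar test statistic using a two-sided type I error rate of 0.05". SAP 7.3 carries the same procedure and level over to the key secondary endpoint.

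**Pain.** Protocol 8.7.4 and SAP 7.4 both specify an ANCOVA with treatment as fixed effect and baseline as covariate, at Weeks 22, 24 and 26. Neither section states a significance level or a sidedness. SAP 7.4 treats FLACC-R scores (under 6 years) descriptively, so in the SAP the test concerns VAS only.

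**Sample size.** Protocol 8.3 and SAP 3.1.3 plan on two-sided 5%.

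**The concern.** A default clause decides the level of every test that does not set its own. The pain ANCOVA is such a test, and it belongs to a declared secondary endpoint. Under the protocol it is judged at 1-sided 5%, under the SAP at 2-sided 5%. The looser level allows twice the false-positive rate in favour of B-VEC.

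Protocol 8.7.1 defers detailed methods to the SAP, but neither document says which prevails when they disagree, and the SAP does not record a departure from the protocol. If a borderline pain result appears, the label put on it depends on which document is read. Sidedness should be settled before the data are unblinded.

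**Working it through.** **1. Which tests fall to the default**

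| Analysis | Protocol | SAP |
|---|---|---|
| Primary (McNemar) | two-sided 0.05 (8.1) | two-sided 0.05 (7.2) |
| Key secondary (McNemar) | two-sided 0.05 (8.2) | as primary, 0.05 (7.3) |
| VAS pain ANCOVA | none stated, so 1-sided 5% (8.7.1) | none stated, so 2-sided 5% (section 7) |

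Only the pain row differs.

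**2. The planned sample size, reproduced**

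Inputs from SAP 3.1.3: response 75% and 25%, independent wounds, enumeration rather than a normal approximation.

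- B-VEC healed, placebo not: 0.75 × 0.75 = 0.5625.
- Placebo healed, B-VEC not: 0.25 × 0.25 = 0.0625.
- Discordant: 0.5625 + 0.0625 = 0.625, the SAP's 62.5%.

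Power was obtained by summing the multinomial probabilities of all outcomes that the exact (binomial) McNemar test rejects:

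| Exact test | Power just below | Smallest n with at least 90% power | Power at n = 24 |
|---|---|---|---|
| Two-sided 5% | 0.8882 at n = 23 | 24 (0.9048) | 0.9048 |
| 1-sided 5% | 0.8824 at n = 19 | 20 (0.9025) | 0.9540 |

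The stated 24 pairs are reproduced by the two-sided exact test. With other forms of the two-sided test the smallest n is 21 (uncorrected chi-square), 22 (normal approximation, 21.8 rounded up) or 25 (continuity-corrected). The 1-sided forms tried all need 20 or fewer. The design basis is therefore two-sided, as both documents say.

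**3. The pain threshold under each default**

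The protocol gives no alternative hypothesis for pain. I take the 1-sided direction to be B-VEC better, since 8.7.1 speaks of superiority comparisons.

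- Normal critical value: z(0.95) = 1.645 (protocol) against z(0.975) = 1.960 (SAP).
- t critical value if all 24 subjects give VAS scores (an assumption, because the number aged 6 and above is not stated): 48 wounds less 3 fitted terms (intercept, treatment, baseline) gives df = 45, and t = 1.679 against 2.014.
- If only 13 subjects give VAS scores: 26 − 3 = 23 df, and t = 1.714 against 2.069. The gap hardly depends on this number.

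**4. False-positive rate in favour of B-VEC**

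- Per time point: 5% (protocol) against 5%/2 = 2.5% (SAP).
- At least one of the three weeks, if they were independent: 1 − 0.95³ = 14.3% against 1 − 0.975³ = 7.3%. If the three weeks were perfectly correlated it would stay at 5% against 2.5%. Repeated scores on the same wounds should fall between these.

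**5. Consistency with the confidence interval**

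A two-sided 95% interval from the same model excludes zero exactly when the two-sided p is below 0.05. A result in favour of B-VEC passes the 1-sided 5% test when the two-sided p is below 0.10. So for 0.05 < p < 0.10 the protocol's test is significant while the interval required by the same paragraph of 8.7.1 includes zero.

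**The case against.** The strongest reply is that the 1-sided entry is an isolated slip with little reach. It applies only where nothing else is indicated, and the two endpoints that carry the confirmatory claim are indicated otherwise in both documents. The sample size is two-sided, the intervals in the same paragraph are two-sided, and the SAP, to which the protocol defers for detail, is plainly 2-sided. Pain has no success criterion: SAP 7.3 passes alpha from the primary to the key secondary endpoint and stops there.

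Most of this stands. It limits the consequence to the nominal label on the pain p-values, and it shows which of the two defaults is out of line with the plan. It does not remove the conflict, because no rule of precedence is given and both documents still test pain without a level.

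A reader might go further and infer that the primary threshold is also in doubt, since Protocol 8.1 and 8.2 write a directional alternative ("H1: %CWH in B-VEC > %CWH in Placebo") where SAP 7.2 writes "H1: Prob(B) ≠ Prob(C". The documents do not support that. Protocol 8.1 states the two-sided level in the same section as the directional alternative. The SAP's statistic, (B − C)²/(B + C) on 1 degree of freedom, is non-directional by construction. Naming the direction of interest beside a two-sided level is common practice, and the difference in wording changes neither the test nor the sample size.

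**Conclusion.** The two documents give different default levels, and the difference takes effect on the VAS pain ANCOVA at Weeks 22, 24 and 26. It also reaches any other test left without its own level. For pain results that favour B-VEC, the disputed zone is a two-sided p between 0.05 and 0.10. The z and error rates rest on no assumption beyond the direction of the 1-sided test; the t values also assume the number of subjects with VAS scores.

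The primary and key secondary levels, their test statistics and the 24 pairs are untouched. This is a correction of consistency with a bearing on nominal significance. It is not a flaw in the confirmatory analysis.

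**What to change.** - In Protocol 8.7.1, replace '(1-sided)' with '(2-sided)'. This agrees with SAP section 7, the sample-size basis and the two-sided intervals in the same paragraph.
- In Protocol 8.7.4 and SAP 7.4, state that the pain comparison at each time point is tested at two-sided 0.05.
- Optionally, as editorial harmonisation only, write the alternative in Protocol 8.1 and 8.2 as 'not equal', as in SAP 7.2.

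The cost is a few words in each document. No sample size, power figure or analysis method changes. The edits should be made before unblinding.

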### **8.7.2 Analysis of Primary Efficacy Endpoint**

The primary endpoint of the proportion of DEB primary wound sites with complete wound healing from baseline will be analyzed using the McNemar Test at Weeks 22 and 24 or 24 and 26.

The complete wound healing is defined as complete wound closure from the exact wound area selected at baseline, specified as skin re-epithelialization without drainage. If new neighboring wounds form around the original traced baseline wound during the primary evaluation time points will not be included in the evaluation.

The primary endpoint is defined as wounds that meet any of the following conditions:

- Healed on Week 22 and Week 24, or
- Healed on Week 24 and Week 26.

Only wounds that are healed for at least two (2) consecutive weeks are counted as positive responses.

The mITT population will be used for this primary efficacy analysis. The ITT and PP populations may also be used as part of the sensitivity analyses.

The primary endpoint results will be summarized by treatment and timepoints for all the subjects in mITT population. A listing of these results will also be presented for all the subjects in the ITT population.

### **8.7.3 Analysis of Key Secondary Efficacy Endpoint**

The key secondary endpoint of the proportion of primary wound sites with complete wound healing from baseline, will be analyzed using the McNemar Test at Weeks 8 and 10 or 10 and 12.

The complete wound healing is defined as complete wound closure from the exact wound area selected at baseline, specified as skin re-epithelialization without drainage. If new neighboring wounds form around the original traced baseline wound during the secondary evaluation time points these areas will not be included in the evaluation.

The primary endpoint is defined as wounds that meet any of the following conditions:

- Healed on Week 8 and Week 10, or
- Healed on Week 10 and Week 12.

Only wounds that are healed for at least two (2) consecutive weeks are counted as positive responses.

The ITT population will be used for this primary efficacy analysis. The PP populations may also be used as part of the sensitivity analyses.

The key secondary endpoint results will be summarized by treatment and timepoints for all the subjects in ITT population. A listing of these results will also be presented for all the subjects in the ITT population.

#### **8.7.4 Analysis of Secondary Efficacy Endpoint**

The following secondary endpoint will be analyzed using the Analysis of Covariance (ANCOVA) with treatment as the fixed effect and the baseline value as the covariate by the time points.

The mean change from baseline in pain severity VAS score per wound site associated with wound dressing changes at Weeks 22, 24 and 26 for each treated versus placebo for ages 6 and above on the primary wound pair. For ages below 6 years, the FLACC-R scale scores will be used instead of VAS scores.

The ITT population will be used for this primary efficacy analysis. The ITT and PP populations may also be used as part of the sensitivity analyses.

The secondary endpoint results will be summarized by treatment and timepoints for all the subjects in the ITT population. A listing of these results will also be presented for all the subjects in the ITT population.

### **8.8 Safety Analyses**

The safety and tolerability of B-VEC based on the assessment of adverse events, physical examinations, vital signs, and clinical laboratory test results. All safety analysis results will be performed using the safety population.

Adverse events will be coded using the version of MedDRA System Organ Class and Preferred Term available at the start of the trial. Adverse events will be grouped into treatment-emergent adverse events and post-treatment adverse events and will be tabulated by preferred terminology and by body system. Each AE will be counted once for each subject unless it resolves and recurs, in which case it may appear as multiple AEs. Severity, frequency, and relationship of AEs to study intervention will be presented by System Organ Class (SOC) and preferred term. Incidence of target-wound-related adverse events will be summarized by treatment, respectively, for each wound pair.

Listings will be provided for discontinuations, deviations, compliance, AEs leading to discontinuation, and target-wound-related adverse events. AE listings will include severity and relationship to study medication, as well as actions taken.

Tables will be provided summarizing reasons for premature discontinuation, protocol deviations, subject compliance, treatment-emergent AEs (TEAEs), TEAEs of target wound, TEAEs by severity, SAEs, and TEAEs leading to discontinuation.

The prior and concomitant medications will be summarized and listed by treatment. Medications will be coded with WHO Drug and categorized as either prior medications (any medication that was started before the first application of B-VEC) or concomitant medications (medication continued or newly started on or after the date of first application of B-VEC).

Medical/procedural history data collected during Screening or Visit 1 (Week 1), will be summarized by MedDRA System Organ Class and Preferred Term.

Descriptive summary of physical examinations, vital signs, and clinical laboratory tests will be reported along with data listings.

Evaluations of viral shedding, infectivity, COL7 and HSV antibodies will be done descriptively.

Any abnormal lab tests obtained during the study will be listed for individual subjects. Any positive findings of the pregnancy test will be listed.

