
Study Treatment, Duration and Assessments
	
Study Treatment
 
Week 1
 
 
- Following randomization of the matched primary wound pair, wounds will receive one Weekly Treatment in a double-blinded manner.
 
- The Remaining Weekly Dose will be calculated and applied to a maximum of four (4) additional wounds (“Secondary Wounds”). Secondary Wound(s) will receive a Weekly Treatment of B-VEC. The number of Secondary Wound(s) treated will depend on wound area of the Secondary Wound(s). The total dose applied to Secondary Wound(s) is not to exceed the Remaining Weekly Dose.
 
 
Week 2 through 26
 
 
- Subjects will return to the clinical site for assessment of all wounds by the Investigator.
 
- The Primary Wound Pair will receive one Weekly Treatment in a double-blinded manner. However, if one of the wounds in a matched Primary Wound Pair closes completely and there are no open neighboring wounds, as determined by the Investigator during a weekly visit, then that particular wound and its neighboring wound/s will not receive Weekly Treatment that week. Once that particular wound, or its neighboring wound/s, is determined to be open by the Investigator at a weekly visit, Weekly Treatment will continue. If the originally selected primary wound closes, its neighboring wound/s may continue to receive treatment.
 
- If a Secondary Wound is closed completely, as well as its neighboring wound/s, as determined by an Investigator, during a weekly visit, then that particular wound and its neighboring wound/s will not receive Weekly Treatment that week. If the originally selected secondary wound closes, its neighboring wound/s may continue to receive treatment. The total dose applied to secondary wounds is not to exceed the Remaining Weekly Dose.
 
- Subjects will come to clinic for assessment even if the originally selected wounds are closed.
 
 
Safety Follow-up/Early Termination
 
 
- Subjects will return to the clinical site 30 days following the last dose of B-VEC.
 
- Subjects may roll into an Open Label Extension (OLE) Protocol. If subjects do not participate in the OLE Protocol, they will be asked to roll over into a Long-Term Follow-up Protocol (All subjects enrolled in the study who received at least a Weekly Treatment).
 
 
Assessments
 
 
- Safety measures include adverse events, physical examinations, vital signs, and clinical laboratory tests. All safety analyses results will be performed using the safety population. A summary of safety results will be presented for each treatment group.
 

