3.1.3 Number of Subjects and Interim Analysis

With 90% power and a two-sided Type 1 error rate of 5%, 24 subjects (i.e., 24 wound pairs) are required for a McNemar's test, assuming a response rate of 75% among wounds randomized to B-VEC and a response rate of 25% among wounds randomized to placebo. These response rates are supported by the results of a Phase 1/2 study in which the response rates for weeks 10 and 12 were 71% and 83% for active and 33% and 14% for placebo, respectively. Because the sample size calculation assumes no correlation within subjects, the estimate is conservative. Any positive correlation will cause an increase in power for the sample size of 24. PASS 2020, "Tests for Two Correlated Proportions (McNemar Test)", was used to calculate the sample size. Because of the small n, the multinomial enumeration was used instead of the normal approximation.

If we assume a 75% response rate among wounds randomized to B-VEC and a 25% response rate among wounds randomized to placebo and we assume independence among the wounds within a subject, we expect a total of 62.5% discordant pairs. Under this scenario, 18.75% of the subjects will have positive responses for both wounds and 18.75% will have negative responses for both wounds:

Expected rates of response and non-response, assuming a 75% response rate for B-VEC treated wounds, a 25% response rate for placebo-treated wounds and no correlation between wounds. The off-diagonals correspond to discordant pairs.

		Placebo		
		Response	Non-response	Total
B-VEC	Response	18.75%	56.25%	75.00%
	Non-response	6.25%	18.75%	25.00%
	Total:	25.00%	75.00%	100%

[figure not shown]
Interim analyses will not be performed for this study.

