The number and percentage of subjects reporting a TEAE will be tabulated by system organ class and preferred term; by system organ class, preferred term, and severity (mild, moderate, and severe); and by system organ class, preferred term, and relationship (unrelated or related to treatment). The incidence of TEAEs will be summarized by preferred term, sorted by decreasing frequency in the B-VEC group, for all TEAEs, related TEAEs, serious TEAEs, and TEAEs leading to study drug discontinuation. The number and percentage of subjects reporting a TEAE of wound site reaction (based on the MedDRA higher level term) will be tabulated, preferred term and severity (mild, moderate, and severe). The incidence of serious TEAEs, TEAEs leading to premature discontinuation of treatment dose, and TEAEs leading to a dose interruption of treatment dose will be summarized by system organ class and preferred term. For all analyses of TEAEs, if the same AE (based on preferred term) is reported for the same subject more than once, the AE is counted only once for that preferred term and at the highest severity and strongest relationship to treatment.

In addition, all AEs (including non-TEAEs), serious TEAEs, TEAEs leading to discontinuation of treatment, and TEAEs leading to dose interruption of treatment will be provided in listings, study site, subject, verbatim term, MedDRA system organ class and preferred term, start and end date, seriousness, severity, relationship to the treatment, action taken with treatment and outcome.

Immune response adverse events due to a severe immune response determined by the Investigator to be possibly, probably or definitely related to B-VEC will be summarized by the number and percentage reporting such AEs along with a subject listing.

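### Local adverse events are planned as crude incidence although applications to each primary wound depend on healing, so the tables cannot support statements on tolerability per application

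*Protocol*

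**What the plan says.** **Dosing.** Under the Protocol Synopsis (Study Treatment, Week 2 through 26), if one wound of the pair is closed and has no open neighbors, "then that particular wound and its neighboring wound/s will not receive Weekly Treatment that week". Dosing resumes on reopening. Schedule of Events footnote 16, Protocol 5.1 and SAP 2.2.1 agree. A neighboring wound may still be treated after the original wound has closed, so the site can stay on treatment. The maximum is 26 weekly applications.

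**Observation.** Protocol 6.5.1 records adverse events from the first application to the safety follow-up or early termination visit, for open and closed wounds alike. Events are tied to a target wound only where applicable or possible.

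**Local event summaries.** Protocol 8.8: "Incidence of target-wound-related adverse events will be summarized by treatment, respectively, for each wound pair". SAP 8.1: "The number and percentage of subjects reporting a TEAE of wound site reaction", by preferred term and severity, with a repeated event counted once per subject and preferred term. SAP 8.1 contains no table by wound.

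**Exposure.** SAP 6.3 has an exposure summary by treatment for primary wounds: "The distribution of subjects by the total number of weeks on therapy (0 through 26) will be presented". It also reports compliance from doses received. No adverse event analysis uses either.

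**The concern.** Every subject receives both treatments on the primary pair, and Secondary Wounds receive open-label B-VEC. Subject-level adverse events therefore have no placebo comparator, and the comparison between the two primary wounds is the only placebo-controlled safety contrast in the trial.

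The number of applications in that contrast depends on efficacy: the better a wound heals, the less often it is dosed. With equal observation time and unequal applications, a local reaction that follows application has fewer chances to occur on the better-healing wound. Local reactions are a live question, because Protocol 1.2.2 lists rash and itching among the events associated with topical B-VEC. At stake is whether a lower or equal crude incidence on the B-VEC wound could be read as better or equal tolerability of each application.

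**Working it through.** **1. The plan's own figure.** SAP 3.1.3 states: "With 90% power and a two-sided Type 1 error rate of 5%, 24 subjects (i.e., 24 wound pairs) are required for a McNemar's test". The healing rates behind this are 75% for the B-VEC wound and 25% for the placebo wound. With zero correlation, the discordant probabilities are 0.75 × 0.75 = 0.5625 and 0.25 × 0.25 = 0.0625. Enumerating the exact McNemar test at two-sided 0.05 gives power of 88.8% at 23 pairs and 90.5% at 24, so the stated 24 reproduces. This matters here only as the source of the 75% and 25%. The documents give no closure timing, no local event rate and no expected application count, so everything below rests on assumptions.

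**2. Applications per wound.** Suppose a wound is dosed at every visit through week w. After that it is closed at a share s of visits (0.75 B-VEC, 0.25 placebo), and a share h of those closed visits is still dosed because a neighbor is open:

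n = w + (26 − w) × [1 − s(1 − h)]

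For w = 8 and h = 0: B-VEC 8 + 18 × 0.25 = 12.5; placebo 8 + 18 × 0.75 = 21.5; ratio 1.72.

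**3. Crude incidence at equal risk.** With the same risk r per application on both wounds, incidence = 1 − (1 − r)^n. The table uses r = 2% as an illustration.

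**4. Break-even.** B-VEC shows the same crude incidence as placebo when its risk per application is 1 − (1 − r)^(n placebo / n B-VEC). The table gives this as a multiple of r.

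| Dosed at every visit through | Applications, B-VEC v placebo (h = 0) | Ratio | Crude incidence, r = 2% | Break-even multiple | Ratio if h = 0.5 |
|---|---|---|---|---|---|
| Week 1 | 7.25 v 19.75 | 2.72 | 13.6% v 32.9% | 2.68 | 1.38 |
| Week 4 | 9.5 v 20.5 | 2.16 | 17.5% v 33.9% | 2.13 | 1.31 |
| Week 8 | 12.5 v 21.5 | 1.72 | 22.3% v 35.2% | 1.71 | 1.23 |
| Week 12 | 15.5 v 22.5 | 1.45 | 26.9% v 36.5% | 1.45 | 1.17 |
| Week 22 | 23 v 25 | 1.09 | 37.2% v 39.7% | 1.09 | 1.04 |

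If h = 1, both wounds get 26 applications and the ratio is 1.0 in every row.

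In counts, for the Week 8 row at r = 2%, 5.4 of 24 B-VEC wounds and 8.5 of 24 placebo wounds are expected to have an event at equal risk. If B-VEC carried 1.5 times the placebo risk per application, 7.6 B-VEC wounds would be expected, still below 8.5.

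**5. Which rate to use.** Suppose both wounds have the same background rate b per wound-week, unrelated to dosing. Over 26 weeks each has 26b events. Dividing all events by applications (Week 8 row) gives 26b/12.5 = 2.08b against 26b/21.5 = 1.21b, a spurious 1.72-fold excess for B-VEC. Counting only events from dosed weeks gives 12.5b/12.5 against 21.5b/21.5, a ratio of 1.0. The numerator therefore has to be limited to dosed weeks.

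**The case against.** The strongest reply is that the regimen under test has the pauses built in. Crude incidence per wound over a common window is a valid description of that regimen, and the planned summary is descriptive, with no test and no stated tolerability claim. This stands. A reader might infer that the crude comparison is invalid, or biased for every purpose; the documents do not support that. It falls short only for a statement about risk per application.

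Second, healed does not mean undosed. The 75% and 25% are endpoint response rates for the original wound area, whereas dosing stops only when the neighbors are closed too. This also stands, and it is why the ratio can fall to 1.0. Treating neighbors is partly at the Investigator's discretion, however, so the gap cannot be presumed absent.

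Third, SAP 6.3 shows exposure by treatment, and events will be listed. This stands in part. Weeks on therapy is not defined as applications given, and the listing fields in SAP 8.1 include event dates but not the wound, so the reader would have to make the link unaided.

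Fourth, a rate per application can mislead against B-VEC. Step 5 shows that it does if every event is charged to the last application before onset. This stands and shapes the fix.

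**Conclusion.** The point holds in a limited form. If B-VEC heals more wounds than placebo, the planned local summaries can understate its risk per application relative to placebo, and no planned analysis would correct for that. With the planning rates taken as closure shares and no dosing of neighbors, the placebo wound gets 1.45 to 2.16 times as many applications if pauses begin after Weeks 12 to 4. The assumed patterns together span 1.0 to 2.7. An excess risk on B-VEC above the exposure ratio would still show in the crude figures.

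Two stronger readings are not supported. A reader might take 2.7 as the expected distortion, but it requires 75% closure from Week 2 and no dosing of neighbors, and the documents state neither. A reader might also infer that B-VEC is more irritating than the placebo gel; nothing in the documents shows this. The point concerns what the tables can show. It affects no efficacy result, error rate or safety decision rule, and is a cheap improvement.

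**What to change.** 1. Carry the tabulation of target-wound adverse events by wound and treatment from Protocol 8.8 into SAP 8.1, which now counts only subjects.
2. Beside the crude incidence, report for each treatment the number of applications per primary wound, and the target-wound events with onset after an application and before the next scheduled weekly visit, per 100 applications. State the cut-off for the Week 26 application, which has no following weekly visit.
3. Show events arising in undosed weeks separately, so that background and late-onset events are neither lost nor charged to an application.
4. Keep crude incidence as the regimen-level summary. Use the dosed-week rate only for statements on tolerability per application.

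The doses received are already counted for compliance in SAP 6.3, so no dosing, visit or data collection changes. The cost is one small extra table. It will be imprecise with 24 pairs, and it depends on attributing events to a wound, which Protocol 6.5.1 asks for only where possible; the number of unattributed events should be shown with it.
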